### 2.2 TRIAL OBJECTIVES

The objective of this trial is to investigate the efficacy, safety, and tolerability of linagliptin 5 mg given orally once daily compared to placebo as add-on therapy for 24 weeks to stable basal insulin treatment in elderly patients, **60** years of age and older, with T2DM with insufficient glycaemic control (i.e., HbA1c of **7.0%** to 10%). Stable background therapy of metformin and/or alpha-glucosidase inhibitors is also allowed.

In addition, this trial will assess if linagliptin reduces the risk of hypoglycaemia when added to background basal insulin therapy. The treatment duration of this trial (24 weeks) will enable assessment of the clinically relevant endpoint of a decrease in HbA1c, a well-accepted measurement of chronic glycaemic control.

For a description of the endpoints chosen and statistical analyses to assess these objectives, refer to [Section 5](#) and [7](#).

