### Criteria for hypoglycaemic events

Every episode of FPG or blood glucose (by HBGM device) below **or equal to** 70 mg/dL (3.9 mmol/L) should be documented as a hypoglycaemic event in the eCRF with the respective time and date of occurrence.

Symptomatic, severe, and hypoglycaemias with FPG or blood glucose values < 54 mg/dL (< 3.0 mmol/L) should be documented as an AE of "hypoglycaemic event". Data related to these hypoglycaemic events [i.e., symptomatic, severe, and hypoglycaemias with FPG or blood glucose values < 54 mg/dL (< 3.0 mmol/L)] will be collected on a specific eCRF and included in the clinical trial report.

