## 7. STATISTICAL METHODS AND DETERMINATION OF SAMPLE SIZE

### 7.1 STATISTICAL DESIGN - MODEL

The objective of the current trial is to investigate the efficacy, safety and tolerability of linagliptin compared to placebo given for 24 weeks as add-on therapy to a stable background of basal insulin, metformin (optional), and/or alpha-glucosidase inhibitors (optional) in elderly patients ( $\geq 60$  years of age) with T2DM and insufficient glycaemic control (i.e., HbA1c of 7.0% to 10%). It is planned to show superiority of linagliptin to placebo for the primary endpoint, the change from baseline in HbA1c (HbA1c after 24 weeks of treatment minus HbA1c at baseline), followed by a decrease in the proportion of patients experiencing at least one confirmed hypoglycaemic event during 24 weeks of treatment, in a hierarchical manner.

HbA1c will be measured in the unit of percent (%) at all clinical visits. A mixed model for repeated measures (MMRM) will be used to compare the change from baseline in HbA1c after 24 weeks of the treatments. The model will include treatment, baseline HbA1c, baseline insulin dose, week, week by baseline HbA1c interaction, and week by treatment interaction.

With regard to efficacy and safety endpoints, the term “baseline” refers to the last observed measurement prior to administration of any randomised study medication.

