### 7.4 HANDLING OF MISSING DATA

#### 7.4.1 Efficacy endpoints

In the primary analysis, if a patient misses a visit, the missing data will not be imputed. The mixed effect model will handle missing data based on a likelihood method under the "missing at random assumption". Following the intention-to-treat (ITT) principle, every randomised patient with at least baseline and one on-treatment measurement will be included in the analysis.

If rescue therapy is initiated, HbA1c and FPG values after rescue will be set to missing and the missing data handled as above (OC or LOCF), according to the analysis strategy.

**For the analysis of hypoglycaemia endpoints, the available data of all patients in the TS will be analysed (OC approach) and no imputation performed.**

For binary endpoints including an HbA1c response criterion, non-completer's considered failures (NCF) approach will be used, i.e., patients who discontinue from the trial prematurely and have no Week 24 HbA1c value will be considered as non-responders.

Methods to handle any other exceptional cases will be considered before unblinding the data and will be applied in a manner consistent with other trials of this type. The evaluability of patients with deviations from the protocol likely to confound the treatment response will be decided prior to unblinding.

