5.2 SECONDARY ENDPOINTS

5.2.1 Key secondary endpoints

There are no key secondary endpoints in this trial.

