5.2.2 Secondary endpoints

Secondary endpoints are the following:

- Proportion of patients experiencing at least one hypoglycaemia accompanied by a glucose value during 24 weeks of treatment. Hypoglycaemia accompanied by a glucose value is defined as
 - any investigator reported asymptomatic hypoglycaemic event or AE with a reported blood glucose measurement less than 54 mg/dL (<3.0mmol/L)
[*AE.SYMI=0 and ((AE.GLUCOSE <54 and AE.LABU=232) or (AE.GLUCOSE <3.0 and AE.LABU=301))*]
or
[*HYPOASYM.GLUCOSE <54 and HYPOASYM.LABU=232) or (HYPOASYM.GLUCOSE <3.0 and HYPOASYM.LABU=301)]*
 - or
 - any investigator reported symptomatic hypoglycaemic AE confirmed by a reported blood glucose measurement less than or equal to 70 mg/dL (≤ 3.9 mmol/L)
[*AE.SYMI=1 and ((AE.GLUCOSE ≤70 and AE.LABU=232) or (AE.GLUCOSE ≤3.9 and AE.LABU=301))*]
 - or
 - a severe hypoglycaemic AE, i.e.,, an event that requires the assistance of another person to actively administer carbohydrates or glucagon because the patient is unable to take the substance on his or her own.
[*AE.ASSIST=1*]

[figure not shown]
Note: If another person hands the carbohydrate or glucagon to the patient without having to actively administer the substance because the patient is able to take the substance on his or her own, the hypoglycaemic AE does not qualify as severe.

[figure not shown]
Note:

[figure not shown]
[figure not shown]
- (i) Hypoglycaemias are counted only once, i.e., a severe episode that has also symptoms indicated on the CRF is counted only once.
- (ii) If *AE.SYMI* is missing and $((AE.GLUCOSE < 54 \text{ and } AE.LABU=232) \text{ or } (AE.GLUCOSE < 3.0 \text{ and } AE.LABU=301) \text{ and } AE.ASSIST \neq 1)$, then the patient is considered for this analysis.

If *AE.SYMI* is missing and $[((AE.GLUCOSE \geq 54 \text{ and } AE.LABU=232) \text{ or } (AE.GLUCOSE \geq 3.0 \text{ and } AE.LABU=301) \text{ or } AE.ASSIST \neq 1)]$, then the patient is not considered for this analysis.

- Proportion of patients with HbA_{1c} on treatment <8.0% after 24 weeks of treatment.
- Proportion of patients with HbA_{1c} on treatment <7.0% after 24 weeks of treatment.
- Proportion of patients with HbA_{1c} lowering by at least 0.5% after 24 weeks of treatment.
- Change from baseline in FPG (mg/dL) after 24 weeks of treatment.

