6.3 PATIENT SETS ANALYSED

- **Randomised set (RS):**
This patient set includes all randomised patients, whether treated or not.
- **Treated set (TS):**
This patient set includes all patients who were dispensed study medication and were documented to have taken at least one dose of investigational treatment.
- **Full analysis set (FAS):**
This patient set includes all patients randomised in the TS who have a baseline and at least one on-treatment HbA_{1c} value.
- **FAS-completers-24 (FASC24):**
This patient set includes all patients in the FAS who complete a minimum treatment duration of 149 days, did not prematurely discontinue the trial and have an available HbA_{1c} measurement within the time window for the Week 24 visit (Visit 98 for non-Japanese and Visit 7 for Japanese patients up to day 176). This analysis set is not required for the analysis at Week 52. See [Table 6.7: 1](#).
- **Per protocol set (PPS):**
This patient set includes all patients in the FAS who do not have any IPVs relating to efficacy, cf. [Table 6.2: 1](#).

Table 6.3: 1 Patient sets analysed

Class of endpoint	Patient set			
	TS	FAS	PPS	FASC24
Primary endpoint		Primary analysis	Sensitivity analysis	Sensitivity analysis
Secondary and further endpoints		X		
Safety endpoints	X			
Demographics	X			
Baseline efficacy variables		X		

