7.5.2 Secondary endpoints

Proportion of patients with at least one hypoglycaemia accompanied by a glucose value during 24 weeks of treatment

Logistic regression for the proportion of patients experiencing at least one hypoglycaemia after 24 weeks will be performed on the FAS (OC); all on-treatment hypoglycaemias will be considered:

- up to drug stop date if a patient prematurely discontinues (Japanese patients that prematurely discontinue prior or at day 175)

- up to trial medication stop date – 1 if a non-Japanese patient does not prematurely discontinue
- up to day 175 if a Japanese patient does not prematurely discontinue prior day 176.

The model will include *treatment* as fixed effect and *baseline HbA_{1c}* and *baseline daily basal insulin dose* as linear covariates.

Frequencies regarding the number and percentage of patients experiencing at least one hypoglycaemia accompanied by a glucose value during 24 weeks in each treatment group will also be presented based on FAS(OC) .

Proportion of patients with HbA_{1c} on treatment <8.0% after 24 weeks of treatment

Logistic regression for the patients achieving HbA_{1c} <8.0% at Week 24 will be performed on FAS (NCF); patients who do not complete 24 weeks of treatment will be considered non-responders. The model will include *treatment* as fixed effect and *baseline HbA_{1c}* and *baseline daily basal insulin dose* as linear covariates. Patients with baseline HbA_{1c} <8.0% will be excluded from the analysis.

A frequency table with the number and percentage of patients with HbA_{1c} <8.0% at Week 24 in each treatment group will be also be presented based on FAS (NCF).

Proportion of patients with HbA_{1c} on treatment <7.0% after 24 weeks of treatment

Logistic regression for the patients achieving HbA_{1c} <7.0% at Week 24 will be performed on FAS (NCF); patients who do not complete 24 weeks of treatment will be considered non-responders. The model will include *treatment* as fixed effect and *baseline HbA_{1c}* and *baseline daily basal insulin dose* as linear covariates. Patients with baseline HbA_{1c} <7.0% will be excluded from the analysis.

Frequencies regarding the number and percentage of patients with HbA_{1c} <7.0% at Week 24 in each treatment group will be also be presented based on FAS (NCF).

Proportion of patients with HbA_{1c} lowering by at least 0.5% after 24 weeks of treatment

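### The SAP analyses the secondary hypoglycaemia endpoint on the FAS, whereas the protocol assigns it to all treated patients

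*SAP*

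**What the plan says.** Protocol section 7.4.1 has a rule specific to these endpoints: "For the analysis of hypoglycaemia endpoints, the available data of all patients in the TS will be analysed (OC approach", with no imputation. Under SAP section 6.3 the TS needs only one documented dose of study treatment.

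SAP section 7.5.2 uses another set: "Logistic regression for the proportion of patients experiencing at least one hypoglycaemia after 24 weeks will be performed on the FAS (OC". The frequency table for the same endpoint is also on the FAS, and Table 6.3: 1 has a single row placing all secondary and further endpoints there. SAP section 6.3 defines the FAS as follows: "This patient set includes all patients randomised in the TS who have a baseline and at least one on-treatment" HbA1c value.

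On the endpoint's standing, protocol section 2.2 states that "this trial will assess if linagliptin reduces the risk of hypoglycaemia when added to background basal insulin therapy". Protocol section 7.1 still puts it after the primary endpoint, as the proportion of patients "experiencing at least one confirmed hypoglycaemic event during 24 weeks of treatment, in a hierarchical manner". SAP section 5.2.1 says: "There are no key secondary endpoints in this trial".

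**The concern.** Having an on-treatment HbA1c value is a sensible entry condition for an HbA1c analysis. It is not needed to know whether a patient had a hypoglycaemia. Applied to this endpoint, it excludes randomised and treated patients on the basis of something that happens after randomisation.

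The patients at risk of exclusion are mainly those who stop before the first scheduled on-treatment HbA1c, at Week 6, and have no timely Visit 98. Some of them may have stopped because of hypoglycaemia, which protocol section 3.3.4.1 lists as a reason for discontinuation. The exclusion can therefore depend on the outcome being compared, and could differ between arms.

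At stake is the between-arm comparison for the trial's hypoglycaemia question, plus the practical matter that two governing documents prescribe different denominators for it.

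**Working it through.** **Step 1. The two texts side by side**

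| Item | Protocol | SAP |
|---|---|---|
| Set for this endpoint | TS (7.4.1) | FAS, for both the regression and the frequency table (7.5.2; Table 6.3: 1) |
| Condition beyond one dose | none | baseline HbA1c and at least one on-treatment HbA1c (6.3) |
| Missing data | observed cases, no imputation | observed cases |

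The mismatch needs no calculation.

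**Step 2. Who leaves.** The flow chart schedules the first on-treatment HbA1c at Visit 4 (Week 6, Day 43). SAP section 6.7 accepts HbA1c values up to 7 days after drug stop. Protocol section 6.2.2 requires Visit 98 at premature discontinuation. A treated patient with a baseline value is therefore lost only by stopping before any on-treatment HbA1c and having none within those 7 days. Most early stoppers should stay in the FAS.

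**Step 3. Does another TS output replace it?** SAP section 7.8 puts all safety analyses on the TS. Protocol section 5.2.2.1 instructs: "Symptomatic, severe, and hypoglycaemias with FPG or blood glucose values < 54 mg/dL (< 3.0 mmol/L) should be documented as an AE". If sites follow this, the SAP 7.8.1 category of hypoglycaemic AEs with glucose ≤70 mg/dL or severe nearly matches the endpoint. Two differences remain:
- The endpoint counts "any investigator reported asymptomatic hypoglycaemic event or AE with a reported blood glucose measurement less than 54 mg/dL", and so includes events entered only on the separate non-AE page. The AE category does not.
- The TS logistic regression in 7.8.1 models any investigator-defined hypoglycaemic AE, not this composite.

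**Step 4. The plan's own figure.** The only stated power is for HbA1c: 150 per arm, difference 0.77, SD 1.2, two-sided 5%, power >99%. The noncentrality is 0.77 / (1.2 × √(2/150)) = 5.56, giving 99.98%, so the figure reproduces. It does not bear on the hypoglycaemia endpoint, for which no power is legible.

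**Step 5. Illustration of size.** Event rates and numbers removed are assumptions; 150 per arm is the planned number. With a/n₁ events on linagliptin and b/n₂ on placebo:

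OR = [a/(n₁−a)] / [b/(n₂−b)], SE(log OR) = √[1/a + 1/(n₁−a) + 1/b + 1/(n₂−b)], two-sided Wald p from log OR / SE, unadjusted.

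- TS 45/150 vs 54/150: (45/105)/(54/96) = 0.762, 95% CI 0.47 to 1.23, p = 0.27.
- TS 15/150 vs 23/150: (15/135)/(23/127) = 0.614, 95% CI 0.31 to 1.23, p = 0.17.

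Now remove k patients per arm, with removed events equal between arms or differing by one:

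| Start | k | Equal events removed | One more removed in placebo | One more removed in linagliptin |
|---|---|---|---|---|
| OR 0.762 | 2 | 0.756–0.761 | 0.781–0.783 | 0.734–0.736 |
| OR 0.762 | 4 | 0.750–0.759 | 0.775–0.782 | 0.727–0.735 |
| OR 0.614 | 2 | 0.582–0.613 | 0.632–0.646 | 0.552–0.568 |
| OR 0.614 | 4 | 0.545–0.612 | 0.599–0.645 | 0.513–0.567 |

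For example, removing 2 per arm with one event lost on linagliptin and none on placebo gives (44/104)/(54/94) = 0.736. Across the first pair p is 0.21 to 0.32; across the second, 0.09 to 0.22.

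**Step 6. An extreme case.** TS 45/150 vs 60/150 gives OR 0.643, p = 0.069 (chi-square without continuity correction). Removing three linagliptin patients who all had events gives (42/105)/(60/90) = 0.600, p = 0.038. Removing three linagliptin patients without events gives (45/102)/(60/90) = 0.662, p = 0.091. One-sided loss of this kind can cross 0.05 when the result starts close to it. This shows sensitivity; it is not an expected outcome.

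**Step 7. Precision.** If 1% to 5% of 300 patients are lost, that is 3 to 15 patients. At assumed rates of 40% vs 30%, power falls from 44.2% to between 43.9% and 42.4%. The loss of precision is negligible; selective loss is the issue.

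**The case against.** The strongest reply is that little is hidden. Besides the AE categories, SAP section 7.8.1 plans TS tables of patients with any hypoglycaemia, whether recorded as an AE or as a non-AE asymptomatic event, and of asymptomatic events from both sources. Hypoglycaemic patients outside the FAS would be counted there by arm. The gap for asymptomatic events below 54 mg/dL arises only where sites do not record them as AEs. This stands as mitigation. However, the visible text gives those overview tables no 54 mg/dL cut, and none of them is the endpoint's treatment comparison.

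Second, a SAP may change a planned analysis. Several rows of SAP section 4 are redacted, SAP section 7.6 is absent from the public text, and protocol section 7.3.2 is incomplete. A declared change, or a TS run of this endpoint, could sit there. For that reason nothing is claimed here about whether the change was declared. The two visible current texts still disagree.

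Third, the hierarchical wording in protocol section 7.1 looks residual: section 7.2 states one hypothesis, section 7.6 powers HbA1c only, and the SAP has no key secondary endpoint. That is fair, and it lowers the endpoint's confirmatory weight. The objective in protocol section 2.2 remains.

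Finally, materiality is unproven. That is correct, and the rating reflects it.

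**Conclusion.** The concern holds. The protocol and SAP assign different analysis sets to the secondary hypoglycaemia endpoint, and the SAP's set can drop treated patients and their events through a condition met only after randomisation. Confidence in the mismatch is high.

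Importance is minor to moderate. That the group is small is a judgement, resting on the Visit 98 requirement and the 7-day HbA1c window; the documents give no count of treated patients outside the FAS. The direction of any bias is unknown. In the scenarios with nearly balanced loss the odds ratio moves modestly and no p-value crosses 0.05; only a deliberately one-sided case does. All of these rest on assumed rates and unadjusted 2×2 tables. The primary HbA1c conclusion is not affected. The point should be fixed because it concerns a stated objective and costs very little.

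**What to change.** - In SAP section 7.5.2, run the hypoglycaemia logistic regression and frequency table on the TS as randomised, in line with protocol section 7.4.1. Split the secondary-endpoint row of Table 6.3: 1 so that this endpoint sits under the TS.
- Keep the FAS run as a sensitivity analysis if wanted. If the sponsor has a reason to keep the FAS as the main set, SAP section 4 should record and justify the departure from the protocol.
- Report, by arm, the number of TS patients outside the FAS and how many of them had an event.
- State one event window for this endpoint. SAP section 6.7 counts hypoglycaemia up to 7 days after drug stop, while section 7.5.2 ends at drug stop for early discontinuers and one day before it for non-Japanese completers. The TS and FAS runs should count the same events.
- TS patients missing baseline HbA1c or baseline basal insulin dose will still leave the adjusted model, since both are covariates. Keep them in the frequency table and report their number.

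The cost is SAP wording, a changed population flag for this endpoint, one short count table and, if wanted, one sensitivity run. Hypoglycaemic events are already recorded for treated patients, so nothing new has to be collected.

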7.7 EXTENT OF EXPOSURE

Exposure to trial medication will be calculated in days as (trial medication stop date – trial medication start date +1) and will be tabulated as a frequency table with categorised treatment duration. In addition, median exposure and the number of patient years of exposure will be given per treatment (calculated as the sum of days over all patients per treatment group divided by 365.25). This table will additionally be produced at Week 52 for Japanese patients.

7.8 SAFETY ANALYSIS

All safety analyses will be performed on the TS.

The analysis will be based on data collected up 24 weeks at DBL. For non-Japanese patients an additional residual period of 7 days is added to the drug stop data.

For Japanese patients, all AEs up to and including day 175 are considered. An additional residual period of 7 days is added for Japanese patients that prematurely discontinue prior or at day 175.

Any data up to day 176 inclusive that is updated or entered after DBL will be summarised in the analysis including data up to 52 weeks only.

7.8.1 Adverse events

Unless otherwise specified, the analyses of AEs will be descriptive in nature. All analyses of AEs will be based on the number of patients with AEs and NOT on the number of AEs.

Furthermore, for analysis of AE attributes such as duration, severity, etc. multiple AE occurrence data on the CRF, will be collapsed into AE episodes provided that all of the following applies:

- The same MedDRA lowest level term was reported for the occurrences.
- The occurrences were time-overlapping or time-adjacent (time-adjacency of 2 occurrences is given if the second occurrence started on the same day or on the day after the end of the first occurrence).
- Treatment did not change between the onset of the occurrences OR treatment changed between the onset of the occurrences, but no deterioration was observed for the later occurrence.

For further details on summarisation of AE data, please refer to the guideline 'Handling and summarization of AE data for clinical trial reports and integrated summaries' ([2](#)).

The analysis of AEs will be based on the concept of treatment emergent AEs. That means that all AEs occurring between first drug intake until 7 days after last drug intake will be assigned to the randomised treatment; in these cases the date and time of the AE onset are used. All AEs occurring before first drug intake will be assigned to 'screening' and all adverse events occurring after last drug intake + 7 days will be assigned to 'post-treatment' (for listings only). For details on the treatment definition, see [Section 6.1](#). Japanese patients who did not prematurely discontinue prior or at day 175 do not have a post-treatment period for Week 24 analysis.

According to International Conference on Harmonisation (ICH) E3 ([3](#)) AEs classified as 'other significant' will include those non-serious adverse events with

- 'action taken = discontinuation' or 'action taken = reduced', or

- marked haematological and other lab abnormalities or lead to significant concomitant therapy as identified by the Clinical Monitor/Investigator at a Blinded Report Planning Meeting.

An overall summary of AEs will be presented. In addition, the frequency of patients with adverse events will be summarised by treatment, primary system organ class and preferred term. Separate tables will be provided for patients with other significant adverse events according to ICH E3 (3) for patients with serious adverse events, AELDs, AEs by severity, and AEs by outcome.

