**Proprietary confidential information.**

© 2015 Boehringer Ingelheim International GmbH or one or more of its affiliated companies. All rights reserved.

This document may not - in full or in part - be passed on, reproduced, published or otherwise used without prior written permission.

evaluation. This includes adverse events that start before first study medication intake and deteriorate under treatment. Other adverse events will be assigned either to the screening, run-in, or follow-up phase as appropriate. All adverse events, including those persisting after trial completion at the Post-Treatment Visit (Visit 99), will be followed-up for up to 7 days. The investigative staff should confirm if continuing adverse events have resolved or have been sufficiently characterised.

The end of the trial is defined as “last patient out”, i.e., last visit completed by the last patient.

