### Worsening of the underlying disease or other pre-existing conditions

Worsening of the underlying disease or of other pre-existing conditions will be recorded as an AE or SAE (if SAE criteria are met) in the eCRF.

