### 7.3.3 Safety analyses

All safety data will be displayed and analysed using descriptive statistical methods. Depending on the character of the individual safety endpoint, the most appropriate way to summarize the results as frequency tables for categorical data or descriptive statistics for continuous data will be used. No formal inferential analysis is planned for safety comparison.

AEs will be coded using the Medical Dictionary for Drug Regulatory Activities (MedDRA) coding dictionary. All events with an onset after the first dose of study medication up to a period of seven days after the last dose of study medication will be assigned to the treatment phase for evaluation. This includes AEs that start before first study medication intake and deteriorate under treatment. Other AEs will be assigned either to the screening, run-in, or follow-up phase as appropriate. Safety analyses will be performed on the TS, with patients assigned to the treatment they were randomised to. Additional listings based on actual treatment at onset of AE will be produced for patients who receive incorrect treatment at any point throughout the trial.

Laboratory values taken after the first dose of randomised treatment up to a period of seven days after the last intake of treatment will be assigned to the treatment phase for evaluation. Laboratory values will be compared to their reference ranges and frequency tables will be provided for the number of patients within and outside the reference range.

Changes from baseline in blood pressure and pulse rate will be summarised by treatment group.

Further details on the safety analysis will be specified in the TSAP.

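### SAP 7.8.1 assigns adverse events by onset alone and omits the protocol's rule that a pre-dose event worsening on treatment counts in the treatment phase

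*SAP*

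**What the plan says.** Protocol Section 7.3.3 places in the treatment phase all events with onset from the first dose to seven days after the last, and then adds: "This includes AEs that start before first study medication intake and deteriorate under treatment". Protocol Section 3.1 has the same rule: "This includes adverse events that start before first study medication intake and deteriorate under treatment". For everything else, Section 7.3.3 says: "Other AEs will be assigned either to the screening, run-in, or follow-up phase as appropriate".

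SAP Section 7.8.1 bases the analysis on treatment-emergent events. Events occurring between first intake and 7 days after last intake go to the randomised treatment, and "in these cases the date and time of the AE onset are used". Then "All AEs occurring before first drug intake will be assigned to" screening. No exception for deterioration is written.

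Three other texts bear on the point:

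- The SAP's rule for collapsing several records into one episode, introduced for attributes such as duration and severity, allows a merge across a treatment change only where "treatment changed between the onset of the occurrences, but no deterioration was observed for the later occurrence".
- Protocol Section 5.2.2.1 states: "Worsening of the underlying disease or of other pre-existing conditions will be recorded as an" AE or SAE.
- SAP 7.8.1 defers to a sponsor document that is not part of this set: "For further details on summarisation of AE data, please refer to the guideline".

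**The concern.** The SAP says that it rests on protocol Section 7, yet the two documents classify the same patient differently. Take a patient whose event starts in run-in and becomes severe on Day 20. The protocol makes this a treatment-phase event. Read literally, the SAP leaves it in screening if the site kept it on one record.

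Such an event would be missing from the treatment-emergent summary and from the serious, severity and leading-to-discontinuation tables. Incidence and intensity of adverse events and withdrawal because of them are the protocol's safety endpoints (Section 5.2.1), and further establishing the adverse event profile is the first rationale listed in Section 2.1. There is also a reconciliation problem. Protocol Section 3.3.4.1 requires the termination form and the adverse event form to agree when a patient is dropped for an event, but the discontinuation table could omit that event.

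**Working it through.** The plan states no figure to reproduce and no arithmetic settles the point. The check is to trace both rules through each way an event can be recorded.

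| Event | Protocol 3.1 and 7.3.3 | SAP 7.8.1, read literally |
|---|---|---|
| Starts between first randomised dose and 7 days after last dose | Treatment phase | Randomised treatment |
| Starts before first dose, does not worsen | Screening or run-in | Screening |
| Starts before first dose; worsening entered as a separate occurrence with on-drug onset | Treatment phase | Randomised treatment (the later occurrence) |
| Starts before first dose, worsens on drug, kept on one record | Treatment phase | Screening |

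**Third row.** The second record qualifies by its own onset. The collapsing rule does not fold it back into the earlier record, because a merge across a treatment change requires no deterioration. The documents agree here.

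**Fourth row.** There is only one onset date and it precedes the first dose. The collapsing rule has nothing to act on, since it concerns multiple records. Nothing in the visible SAP moves the event into the treatment tables. This is the only row in which an event the protocol puts in the treatment phase is lost from it.

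**Can the fourth row occur?** Protocol Section 5.2.2.1 makes worsening of pre-existing conditions reportable, which clearly covers conditions present at baseline. It does not say that an event already open from screening or run-in must be closed and re-entered with a new onset. Section 5.2.2.2 asks for onset date, end date and intensity for each event and refers to the site file for reporting instructions. A single record with a pre-dose onset is therefore possible on the documents available.

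**How long is the pre-dose window?** Events are collected from consent (Section 5.2.2.2). By flow chart footnote A, screening and run-in each last 7 to 14 days:

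- shortest: 7 + 7 = 14 days
- longest: 14 + 14 = 28 days

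Every randomised patient thus has about 2 to 4 weeks in which an event can start and still be open at the first randomised dose.

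**What is first drug intake?** Protocol Sections 4.1.4 and 4.3 use the term study medication for the run-in placebo as well. SAP Table 6.1.1: 1 separates run-in medication from study medication, and SAP 6.7 speaks of randomised medication. SAP 7.8.1 uses neither qualifier. Randomised medication is very probably meant, but the sentence does not say so. Read as run-in placebo, it would move run-in events into the randomised arms.

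**Was a change declared?** The visible rows of SAP Section 4 contain nothing on adverse event assignment. Some rows are redacted.

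**The case against.** A reader might infer that on-drug worsening disappears from all treatment-emergent tables and that an aggravating effect of the drug could not be seen. The documents do not support that. Worsening entered as its own occurrence is counted, the collapsing rule protects it, and the protocol's definition of an adverse event includes exacerbation of a pre-existing condition. The collapsing rule also shows that the SAP's authors had deterioration across a treatment change in mind.

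It can further be argued that the gap may be closed elsewhere. The site file or the sponsor guideline may require a new record for each worsening. The SAP assumes familiarity with the protocol, so its treatment-emergent concept could be read together with protocol Section 7.3.3. The redacted rows of SAP Section 4 may mention the change. Finally, the protocol plans no formal inference on safety, so no test depends on this.

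Most of this stands as a limit on size. It does not remove the conflict. The collapsing rule is written for event attributes and presupposes two records. The guideline and site file cannot be checked here. An explicit SAP sentence sending every pre-dose event to screening is what a programmer would implement, whatever the protocol says. Nor do the redactions allow the opposite inference, that the change was made without being declared.

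**Conclusion.** The conflict holds in limited form. SAP 7.8.1 omits the protocol's deterioration clause, and its literal rule contradicts protocol Sections 3.1 and 7.3.3. The loss is confined to events kept on one record with a pre-dose onset that worsen on treatment.

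The number of such events is unknown. The documents give neither a rate of ongoing events at first dose nor a rate of worsening, so no shift in any table can be derived. The direction is clear: where such events exist, treatment-emergent counts come out too low in whichever arm they fall. The primary endpoint and every efficacy test are unaffected. The conclusion assumes that no unseen instruction forces a new record for each worsening; if one does, the gap closes in practice and only the wording needs repair. The correction should be made before database lock, but it does not threaten the trial's main conclusion.

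**What to change.** In SAP 7.8.1:

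- Add that an event with onset before first randomised intake that deteriorates between first randomised intake and last intake + 7 days is assigned to randomised treatment and dated at the deterioration. The SAP 7.8 Day 175 limit for Japanese patients who continue treatment can stay as it is.
- State that first drug intake means the first dose of randomised medication, not run-in placebo.
- Keep deterioration as the only trigger. Adding others, such as discontinuation without worsening, would take the SAP beyond the protocol rule.

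Before database lock, review a blinded listing of events ongoing at first randomised dose and confirm the assignment of each.

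The cost is two sentences and one listing. The one drawback is that where only a single record exists, the date of worsening may need a site query.
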